### **Analysis of food intake**

Food items were weighed before and after eating to determine the amount of food consumed. Total calorie and energy density (kcal/g) of consumed food was calculated from the product nutrition labels. Changes in food intake in the deprived sleep (DS) session were computed as percentage change from non-sleep deprived baseline (NSD) and tested against zero using one-sample t-tests.

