**2) Aim 2: Determine the link between sleep-dependent olfactory processing and calorie intake.**

Sleep-restriction has been shown to enhance craving and consumption of high-calorie snacks. Here we aim to determine the relationship between altered hormone levels, neural processing of food odors, and enhanced calorie intake. *We hypothesize that fMRI responses in early olfactory and reward-related brain regions will mediate enhanced food craving and calorie intake. Moreover, we predict that brain processes related to resilience will be represented in the dorsolateral prefrontal cortex, and that these processes are characterized by enhanced connectivity with reward-related brain regions.* After the fMRI scanning session, satiated subjects will be given the opportunity to consume high-calorie snacks *ad libitum* in a controlled environment. In addition, subjects' food intake will be recorded for 24 after the scanning session using dietary diaries. We will compute the total calorie intake and compare it between

sleep-deprived and non-deprived states. Critically, we will use neural mediation analyses to determine how the relationship between sleep-dependent changes in hormone levels and enhanced calorie intake is mediated by neural responses to food odors. This will reveal brain regions in which neural processing of food mediates increased food intake, and thereby identify potential therapeutic targets. We also propose to compare subjects that manage to abstain from excess calorie intake in a sleep-deprived state to those that do not. This will identify brain processes that support resilience to enhanced calorie intake. We predict that such processes will be represented in the dorsolateral prefrontal cortex and will be characterized by enhanced inhibitory connectivity with reward-related regions. Identification of these protective mechanisms may inform future clinical studies in obesity, and may help to establish novel treatment and prevention strategies for weight-gain and obesity, specifically in high-risk populations with disrupted sleep-schedules.

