### Secondary endpoints

Secondary endpoints of this proposal are the total calories of food consumed during the ad-libitum food intake phase, subjective ratings of hunger, fullness, prospective food consumption, and satiety using the visual analogue scale, food craving questionnaire, and total calorie intake using the self-reported food intake for 24 h following the fMRI scan.

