*Hormone levels.* As soon as subjects arrive at the imaging center, an intravenous sterile heparin-lock catheter will be inserted in a forearm vein and blood sampling will be initiated by the CRU mobile nurse. We will draw blood every 30 min after arrival, resulting in 5 samples, including a fasted baseline (6 pm), after dinner (6:30 pm), before (7 pm), during (7:30 pm, after the second scanning run), and after the scanning session (8 pm) for leptin and ghrelin analysis. An additional sample will be collected at 7:30 pm time point for 2-AG and 2-OG analysis. Plasma and serum samples will be frozen at  $-80^{\circ}\text{C}$  until assay for ghrelin, leptin, insulin using commercially available ELISA kits, and 2-AG and 2-OG using published procedures (49, 50). Phase of menstrual cycle in women has an impact on these hormonal levels. The 2.5-week washout period will ensure that the blood samples are collected in the same phase of the menstrual cycle

*Ad-libitum food intake.* At the completion of the fMRI scan, participants will be provided with snacks in a

buffet-style setting where they will have *ad libitum* access to food items corresponding to the odors used during fMRI scanning (sweet and savory high-calorie snacks). They will be instructed to consume as much food as they like. To measure food intake, food will be weighed pre- and post- consumption, and calories consumed will be calculated. Because subjects have been provided with dinner before the scanning session, food intake at the buffet will mainly reflect hedonic, rather than metabolic eating (47). *Appetite and hunger ratings.* Subjective food craving, ratings of hunger, fullness, prospective food consumption, and satiety will be measured using a visual analogue scale. These ratings will be acquired on the fMRI scanning day upon arrival, at all blood collection time points, and after the *ad libitum* meal. Subjects will also complete the food craving questionnaire on the day of fMRI scan.

*24 h post-fMRI food intake diary.* Subjects will be instructed to carefully record the food items, quantity consumed, place of consumption, and the food brands, for 24 h following the fMRI scan. We will calculate the total energy, fat and carbohydrate consumption for SD and NSD states.

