#### **DATA AND SPECIMEN MANAGEMENT:**

Sample size is based upon the requirements for group analysis, particularly when random-effects analyses are performed. Random-effects analyses require a minimum of 14 -18 subjects in each group in order to obtain statistically meaningful fMRI effects. Our target subject number also accounts for attrition in the subject pool due to unanticipated claustrophobia, technical/mechanical issues, or other problems during the fMRI session.

For the statistical analyses, comparisons of subjective appetite ratings and calorie intake between the SD and NSD state will be carried out using paired t-tests. Spearman's correlation analysis will be used to test the relation between appetite ratings, neural responses to food odors, and the total calories consumed. Moreover, we will use whole-brain mediation analysis (51) to identify the brain regions in which neural responses to food odors mediate the link between sleep-dependent changes in hormone levels and enhanced calorie intake. To identify brain mechanisms related to resilience, we will compare fMRI responses to food odors between subjects that manage to abstain from excess calorie intake in a sleep-deprived state to those that do not. We will use fMRI connectivity analyses (psychophysiological interaction, PPI (52)) to test the hypothesis that resilience to enhanced food intake in a SD state is associated with enhanced functional connectivity between the dorsolateral prefrontal cortex and reward-related brain regions (53). We will monitor sniffing using a breathing belt and spirometer, and model trial-by-trial sniff parameters will be included as covariates in all fMRI analyses following established procedures to control for respiration-induced effects.

To preserve subject privacy and confidentiality, all research materials (questionnaires, behavioral testing results, and magnetic resonance imaging data) will be coded by a different study code number unique for each subject, in order to keep the identity and personal information of each subject as confidential as possible. This number will be recorded on all testing sheets instead of the subject's

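### The SAP sets an unlisted measure, energy density, beside the protocol's buffet calorie endpoint without ranking the two or saying what happens when a subject eats nothing

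*SAP*

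**What the plan says.** The protocol treats the buffet as a calorie measurement throughout. Its Secondary endpoints section opens: "Secondary endpoints of this proposal are the total calories of food consumed during the ad-libitum food intake phase". The ad-libitum paragraph under Procedures Involved gives the method: "food will be weighed pre- and post- consumption, and calories consumed will be calculated". Under Data and Specimen Management the planned test is that "comparisons of subjective appetite ratings and calorie intake between the SD and NSD state will be carried out using paired t-tests". Energy per gram is not an outcome anywhere in the protocol. The one other intake endpoint is the diary measure, "total calorie intake using the self-reported food intake for 24 h following the fMRI scan".

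The SAP, under Analysis of food intake, computes two buffet quantities: "Total calorie and energy density (kcal/g) of consumed food was calculated from the product nutrition labels". The next sentence gives the test, a one-sample t-test: "Changes in food intake in the deprived sleep (DS) session were computed as percentage change from non-sleep deprived baseline (NSD) and tested against zero". It does not say whether food intake means calories, energy density or both. It gives no order, significance level, multiplicity rule or rule for a session in which nothing is eaten.

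**The concern.** Aim 2 concerns increased calorie intake after short sleep, and only total calories answers that. As the SAP is worded, a null result on calories could sit beside a positive result on kcal/g, and either could be reported as a change in food intake. The reader would have no stated basis for knowing which was meant to decide.

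The ratio also has a narrower meaning than its name suggests. The buffet consists of "food items corresponding to the odors used during fMRI scanning (sweet and savory high-calorie snacks", so energy density describes the mix chosen among those items and nothing else. It is also a quotient of kcal over grams, with no value for a subject who takes no food. Dinner is served before the scan and the buffet follows it, so an empty session is possible. The SAP does not say what would then be done.

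**Working it through.** **Inputs from the documents.** Enrolment is 40 and expected drop-out is 15–25% (Protocol, Number of Local Participants). Completers: 40 × 0.75 = 30 to 40 × 0.85 = 34.

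**Assumptions.** Each intake test is two-sided at 0.05; the SAP states 0.05 only for the imaging analysis. Both measures are tested. The correlation between them and the chance q of eating nothing in a session are unknown, so ranges are shown.

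**The plan's own figure.** There is none to reproduce. The documents give no power, effect size, standard deviation or error rate for food intake; the sample size rests on a minimum for random-effects imaging analyses.

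**Step 1: chance of at least one false positive.** For two independent tests: 1 − 0.95² = 0.0975. For correlated measures, two one-sample t-tests were simulated with no true effect, 40,000 runs per setting:

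| Correlation | 30 completers | 34 completers |
|---|---|---|
| 0 | 0.097 | 0.098 |
| 0.3 | 0.095 | 0.097 |
| 0.5 | 0.090 | 0.090 |
| 0.8 | 0.079 | 0.075 |
| 0.95 | 0.061 | 0.065 |

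So the rate runs from about 6% to 9.75% over these correlations. With a single ranked test it is 5%.

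**Step 2: can the measures disagree?** Take a hypothetical subject who eats 100 g at 3 kcal/g when not deprived and 50 g at 5 kcal/g when deprived.
- Calories: 300 to 250 kcal, a change of 250/300 − 1 = −17%.
- Energy density: 3 to 5 kcal/g, a change of 5/3 − 1 = +67%.

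The subject ate less, yet the ratio rose.

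**Step 3: when is each quantity defined?** SD is the sleep-deprived session, NSD the non-deprived one.

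| Session with no intake | Energy density change | Percentage change in kcal | Paired kcal difference |
|---|---|---|---|
| Neither | defined | defined | defined |
| SD only | undefined | −100% | defined, negative |
| NSD only | undefined | undefined | defined, positive |
| Both | undefined | undefined | 0 |

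The second row matters most. A subject who eats in NSD and nothing in SD is strong evidence against the hypothesis; that subject counts as −100% on calories and disappears from energy density.

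**Step 4: expected losses.** With q independent across sessions, energy density loses n × [1 − (1 − q)²] subjects and percentage change in calories loses n × q. The chance of losing at least one from energy density is 1 − (1 − q)^(2n). Results are for 30 / 34 completers:

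| Assumed q | Lost, energy density | Lost, percentage change in kcal | Chance of losing at least one from energy density |
|---|---|---|---|
| 0 | 0 / 0 | 0 / 0 | 0 |
| 2% | 1.19 / 1.35 | 0.60 / 0.68 | 70% / 75% |
| 5% | 2.93 / 3.32 | 1.50 / 1.70 | 95% / 97% |
| 10% | 5.70 / 6.46 | 3.00 / 3.40 | 99.8% / 99.9% |

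**The case against.** The SAP says only that energy density was calculated. It does not say that it is tested or offered in place of calories, and a descriptive account of snack choice is legitimate. This stands in part: the double test is a permitted reading, not a stated one. But the ambiguity is itself the defect, because the test sentence follows directly and names neither measure.

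Zero intake is conjecture. Subjects are invited to eat freely from snacks matched to their odors, and no rate of empty sessions is reported or predicted. This stands. If everyone eats something, nobody is lost.

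A reader might infer that the ratio removes the very subjects the resilience analysis needs. The documents do not support that. Aim 2 proposes to "compare subjects that manage to abstain from excess calorie intake in a sleep-deprived state to those that do not", which means avoiding excess, not avoiding food. Such subjects normally keep a defined ratio. Only zero eaters are affected, and one who eats nothing when rested but eats when deprived is the opposite of resilient.

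The protocol already lists several unranked secondary endpoints, including diary calories, so singling out this pair may seem selective. That is fair as to multiplicity overall, which this point does not settle. Energy density differs in that the protocol does not list it and it shares an undifferentiated test sentence with the listed endpoint.

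**Conclusion.** The concern holds in limited form. The SAP adds an intake measure that the protocol does not list, leaves it level with the listed one, and gives no zero-intake rule for either. If both are tested at 0.05, the false-positive chance for the buffet question is about 6% to 9.75% rather than 5%. The upper figure is the ceiling for independent tests and should not be quoted as the rate, since calories are the numerator of the ratio and the true correlation is unknown.

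The undefined-value problem is conditional on someone eating nothing, and it is not peculiar to energy density. The SAP's percentage change fails for calories too when NSD intake is zero, so demoting the ratio while keeping that scale would leave the gap open.

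The SAP is written in the past tense, and a reader might infer that the ratio was chosen after the results were seen. The text available neither shows nor excludes that. This is a secondary endpoint, and the point is a cheap improvement, not a threat to the trial's primary conclusions.

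**What to change.** In the SAP, Analysis of food intake:

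- Name total buffet calories as the single main buffet outcome, matching the protocol's Secondary endpoints.
- Test it as the absolute paired difference, SD minus NSD in kcal, using the paired t-test already planned under Data and Specimen Management. This includes zeros and exists for every completer. Percentage change can be kept as description.
- Label energy density exploratory, or test it only after calories are significant.
- Compute energy density in subjects who ate in both sessions, report how many were dropped for no intake in each sleep state, and interpret it only as choice among the snacks offered.

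The cost is a few sentences and no new data. The downside is that energy density cannot be claimed as a confirmatory intake result, unless it is placed second in the testing order and calories are significant first.

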**MULTI-SITE RESEARCH: N/A**

**STUDY TIMELINES:**

Each participant will follow a ~ 6 week within-subject, crossover partial sleep-deprivation protocol to test the effect of sleep deprivation (SD) and non-sleep deprivation (NSD) on neural processing of food odors in sensory and reward related regions (**Fig. 2**). Qualified subjects will be randomly assigned to either participate in the SD or the NSD condition first. Subjects will then undergo a week of sleep stabilization phase to stabilize circadian rhythms for a week. After the sleep stabilization week, the night before the fMRI session, subjects will either sleep normally (NSD, 8 h of sleep between 11 pm and 7 am), or sleep only for 4 h between 1 am and 5 am (SD) at home. All subjects will participate in both sleep conditions (SD and NSD) in randomized order, separated by ~2.5 week washout period. The

evening of the sleep manipulation, subjects will visit the lab to consume dinner and pick up their sleep monitors. We will also provide a take-out breakfast and lunch to be consumed at 8:00 am and 12 noon, respectively. All meals will be provided by the CRU. Subjects will perform an odor-rating task inside the MRI scanner on the same evening. Serial blood samples will be collected for measurement of appetite-regulating hormones. At the completion of the fMRI scan, participants will be provided with snacks in a buffet-style setting where they will have *ad libitum* access to food items corresponding to the odors used during fMRI scanning (sweet and savory high-calorie snacks). They will be instructed to consume as much food as they like. We anticipate to enroll all participants within a 12-month period and plan to complete the study data collection and analyses within a period of 3 years from the date of IRB approval.

**Figure 2. Study design and scanning protocol. A.** Timeline of the sleep-deprivation protocol. All subjects will participate in both sleep conditions (SD and ND), in randomized order. On the scanning day, blood (BD) will be drawn every 30 min. **B.** For each subject, two sweet and two savory high-calorie food odors will be selected and presented during the scanning session, in addition to two non-food odors and trials in which non-odorized air is presented. **C.** Example trial of the fMRI task. After a countdown, an odor is presented, after which subjects have to rate the pleasantness or the intensity of the delivered odor.

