## STUDY ENDPOINTS:

### Primary endpoints

The primary endpoints of this proposal are the analysis of neural representations of high-caloric food odors in early olfactory cortex and food reward regions, and levels of orexigenic hormones using the serial blood samples.

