## PROCEDURES INVOLVED:

We propose to implement a randomized within-subject, crossover partial sleep-deprivation protocol to examine the effects of sleep deprivation (SD) on neural processing of food odors in early sensory and reward-related brain regions. In brief, after a one-week sleep stabilization period, subjects will spend a night either sleep deprived (SD, 4 h of sleep) or with normal sleep (non-SD, NDS, 8 h of sleep) at home. On the next day, fMRI scanning will be conducted at 7 pm after dinner, when sleep-deprivation induced changes in hormonal levels are most prominent (11). Hormone levels will be monitored using serial blood sampling in response to a meal (dinner).

**Sleep-deprivation protocol.** Subjects (N=40) will be randomly assigned to either participate in the SD or the NSD condition first (**Fig. 2A**). Subjects will then undergo a sleep stabilization phase to stabilize circadian rhythms. During this week, subjects will be instructed to keep a regular sleep schedule of 7-9 hours in bed between 10:30 pm and 7:30 am. Participants will abstain from alcohol, caffeine, and drugs in this phase. After the sleep stabilization week, the night before the fMRI session, subjects will either sleep normally (NSD, 8 h of sleep between 11 pm and 7 am), or sleep only for 4 h between 1 am and 5 am (SD) at home. We opted for a partial sleep-deprivation protocol because this situation (late bedtime and early wakeup) is ecologically valid as it reflects the most realistic form of sleep-deprivation in

everyday life. All subjects will participate in both sleep conditions (SD and NSD) in randomized order, separated by a 2.5-week washout period.

*Sleep-monitoring.* To ensure that subjects follow the sleep schedule during the sleep stabilization phase and sleep manipulation days, we will record sleep duration, as well as sleep and wake-up time using a daily sleep diary and wrist actigraphy (ActiGraph, LLC, Pensacola, Florida (45)). Additionally, subjects will rate their subjective sleep quality, alertness, and restfulness every morning using an online questionnaire. Subjects will also rate their subjective sleepiness using the Stanford Sleepiness Scale (46) before the fMRI scan during both the SD and NSD phase. Participants will spend the night of sleep manipulation (both SD and NSD) at home and food will be provided for these days.

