Next, we used these voxel-wise parameter estimates in a searchlight-based, leave-one-run-out cross-validated decoding approach. We decoded food vs. non-food odors from patterns of odor-evoked activity, separately for each of the two sleep sessions. We used The Decoding Toolbox (TDT) to implement the searchlight (Hebart, Gorgen, & Haynes, 2014) and LIBSVM (Chang & Lin, 2011) for the linear support vector machine (SVM) classifier. To test for brain regions that encoded food vs. non-food odors, at each searchlight (sphere with 8 mm radius), we trained a SVM to discriminate between activity patterns evoked by food vs. non-food odors in three of the four runs per session (DS or NDS), and tested it on activity patterns evoked by food vs. non-food from the fourth “left out” run of the same session. The procedure was repeated four times leaving a different run out, and decoding accuracies were averaged and mapped to the center voxel of the searchlight. This procedure was repeated for every voxel within a 10% gray-matter mask (based on SPMs tissue probability map that was inverse-normalized into the individual native space, as described in (Howard & Kahnt, 2018)). The resulting accuracy maps for food vs. non-food odors for DS and NDS sessions were subtracted (DS > NDS), normalized, and smoothed (6mm FWHM). We tested for significant differences between DS and NDS sessions at the group level using voxel-wise one-sample t-tests. Statistical thresholds were set to  $P < 0.05$ , family-wise error (FWE)

small-volume corrected for multiple comparisons at the voxel-level in a functional mask of piriform cortex that was obtained from a one-sample t-test of decoding accuracy for food vs. non-food odors, averaged across sleep sessions.

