### **Analysis of hormones**

Ghrelin, leptin, insulin, and cortisol were measured in blood samples collected at each session. Changes in hormone levels in the deprived sleep (DS) session were computed as percentage change from non-sleep deprived baseline (NSD) and tested against zero using one-sample t-tests.

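### Session order is randomised, but no SD–NSD comparison described in the plan includes it. A period effect would cost power and, with unequal completed sequences, shift the estimate.

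*SAP*

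**What the plan says.** The trial is a two-period crossover. Protocol, Study Timelines: "Qualified subjects will be randomly assigned to either participate in the SD or the NSD condition first". Protocol, Procedures Involved: "All subjects will participate in both sleep conditions (SD and NSD) in randomized order, separated by a 2.5-week washout period".

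The comparisons between the two sessions are described in four places:

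- Protocol, Data and Specimen Management: "comparisons of subjective appetite ratings and calorie intake between the SD and NSD state will be carried out using paired t-tests".
- SAP, Multivoxel pattern analysis: "We tested for significant differences between DS and NDS sessions at the group level using voxel-wise one-sample t-tests".
- SAP, Analysis of food intake: "Changes in food intake in the deprived sleep (DS) session were computed as percentage change from non-sleep deprived baseline (NSD) and tested against zero", by one-sample t-tests.
- SAP, Analysis of hormones: the same percentage-change construction and the same test.

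The covariates named are sniff parameters (protocol) and first-level respiration and motion regressors (SAP). None of them is a group-level term for session order. The method of allocating order is not stated. The SAP's pre-processing section also mentions univariate and connectivity analyses, but the available text does not describe them, so this point covers only the tests listed above.

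**The concern.** Each subject's SD–NSD difference contains the sleep effect plus or minus any systematic change from the first session to the second. A plain one-sample or paired t-test treats that change as noise, which lowers power. If more subjects complete one order than the other, part of the change is also read as a sleep effect.

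Such a change is most plausible for the secondary intake and rating endpoints. The odors are chosen once per subject and the buffet foods correspond to them (Protocol, fMRI scanning protocol and Ad-libitum food intake), so each subject meets the same odors and foods twice. This is an inference; the documents report no period effect. For the primary endpoints, neural responses and hormones, there is less reason to expect one.

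**Working it through.** **Inputs**

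- Completers: 40 enrolled and 15–25% drop-out (Protocol, Number of Local Participants), so 40 × 0.85 = 34 and 40 × 0.75 = 30.
- Sleep effect δ: the protocol gives no effect size, variance or power, so there is no planned figure to reproduce. I assume the effect that a single two-sided 5% paired t-test detects with 80% power: 0.529σ for 30 completers and 0.495σ for 34. Here σ is the standard deviation of the paired difference within a sequence.
- Period effect π (session 2 minus session 1): not in the documents; 0.1σ to 0.75σ assumed.
- Allocation: not stated. I take two cases: simple randomisation, and exact 20/20 with random drop-out.

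**Model.** dᵢ = δ + π·sᵢ + eᵢ, with s = +1 if NSD came first and −1 if SD came first. n₁ and n₂ are the completers in those two orders, and N = n₁ + n₂.

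**Shift of the unadjusted mean.** This is π(n₁ − n₂)/N. At 18/12 with π = 0.5σ it is 0.5 × 6/30 = 0.10σ, and 0.10/0.529 = 19% of the assumed sleep effect. At π = 0.1σ, 0.25σ and 0.75σ it is 0.02σ, 0.05σ and 0.15σ. The direction depends on which order has more completers.

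**Variance in the unadjusted test.** Its expectation is σ² + π²·4n₁n₂/[N(N − 1)]. At 15/15 with π = 0.5σ, in units of σ², this is 1 + 0.25 × 900/870 = 1.26. The standard error is therefore overstated by √1.26 = 1.12, although the mean itself is no more variable. The test becomes conservative (type I error 2.9%) and loses power.

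**Adjusted estimate.** This is the average of the two sequence means, with variance (σ²/4)(1/n₁ + 1/n₂) and N − 2 degrees of freedom. In units of σ² the variance is 0.0333 at 15/15, 0.0347 at 18/12 and 0.0375 at 20/10. The unadjusted mean has 1/30 = 0.0333.

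**Average power, unadjusted / adjusted, 30 completers** (simulation, 400,000 replicates per cell; results for 34 completers are within 0.4 points):

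| π (in σ) | Simple randomisation | 20/20, random drop-out |
|---|---|---|
| 0 | 0.799 / 0.784 | 0.800 / 0.796 |
| 0.1 | 0.797 / 0.786 | 0.797 / 0.796 |
| 0.25 | 0.775 / 0.784 | 0.780 / 0.795 |
| 0.5 | 0.707 / 0.785 | 0.719 / 0.795 |
| 0.75 | 0.610 / 0.784 | 0.622 / 0.795 |

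Break-even is near 0.2σ under simple randomisation and 0.1σ under 20/20. Averaged over allocation, unadjusted type I error is 5% under simple randomisation and at or below 5% under 20/20. Adjusted error is about 5% throughout.

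**Given the realised split.** At 18/12 or 12/18 with π = 0.5σ, unadjusted power is 0.87 or 0.53 according to which order is larger; adjusted power is 0.78 either way. Completed sequences differ by 6 or more in 36–39% of trials under simple randomisation, but in only 2.0–6.5% under 20/20. Unadjusted type I error stays near 5% at 18/12 and reaches 10% only at an extreme split such as 20/10.

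**Percentage change behaves differently.** Suppose there is no sleep effect, no noise and a multiplicative period effect of 1.5. The sequence means are 1.5 − 1 = +50% and 1/1.5 − 1 = −33.3%, so their average is +8.3%, not zero. At a ratio of 1.2 they are +20% and −16.7%, average +1.7%. The sequence term estimates exactly this average. It leaves the bias in place and removes the variance that was masking it.

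I simulated lognormal outcomes with within-subject CV 0.2 and no sleep effect. At 15/15, adding the term to percentage change raises type I error from 6.0% to 13.6% at ratio 1.2, and from about 5% to 49% at 1.5. At ratio 1.2 it helps at 18/12 with NSD-first larger (20% to 11%) and harms at 12/18 (2% to 16%). On the log scale, adjusted error is about 5% in every case.

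**The case against.** The strongest reply is that randomised order with a 2.5-week washout already protects the comparison, so an order term is a refinement and not the correction of an error. On a difference or log scale that stands: averaged over randomisation the estimate is unbiased and type I error is not inflated.

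A reader might infer more: that sleep condition is confounded with order, that false positives are inflated, or that this trial's sequences ended up unequal. The documents support none of these. Order is randomised and no completer counts are given.

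The gain is also modest unless the period effect is large. At 0.1σ the term costs about 1 point under simple randomisation. The 8-point gain needs a period effect about as large as the assumed sleep effect. This stands, and it limits the weight of the point.

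The intake and hormone tests use a ratio, so figures from an additive model do not describe them and adding the term there can do harm. This also stands, and it restricts the fix.

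Finally, the mechanism is weakest for the primary endpoints, and power figures for one 5% test do not carry over to the voxel-wise family-wise-error threshold. That is correct; for those endpoints the term is a safeguard.

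What the reply does not remove is the single-trial shift and the lost efficiency, both of which follow from the algebra if a period effect exists.

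**Conclusion.** The omission holds for every SD–NSD comparison that the documents describe. On a difference or log scale it is a matter of efficiency and of bias given the realised split, not of validity.

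With 30–34 completers and a sleep effect sized for 80% power, adjusting loses up to about 1 power point at a period effect of 0.1σ, gains about 1–2 points at 0.25σ and about 8 at 0.5σ. It also removes a shift of 0.10σ at 18/12 with 0.5σ. All of these sizes rest on assumed period effects and assumed allocation methods. The change is worth making, mainly for intake and ratings, provided the outcome scale is right.

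**What to change.** - **Ratings and calories (protocol) and decoding accuracy (SAP):** add sequence as an uncentred ±1 covariate to the group-level model of the SD–NSD difference and test the intercept. Equivalently, average the two sequence means, with pooled standard deviation and N − 2 degrees of freedom. Do not mean-centre the covariate: the shift then stays in the intercept, and with a 0.5σ period effect type I error is 8.3% at 18/12 and 7.9% at 20/14.
- **Food intake and hormones (SAP):** apply the same model to the SD–NSD difference or to log(SD/NSD), with the scale fixed in advance. Use the difference where zero intake can occur. Do not add the term to percentage change as it stands.
- **Reporting:** state how order was allocated and give completers per sequence. The SAP is written in the past tense; if the unadjusted tests have already been run, report both.

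Cost: one degree of freedom and a re-run of the group-level models, using a variable known for every subject. With no period effect, the power lost is about 0–0.4 points under 20/20 allocation, about 1.5 under simple randomisation, 1–2 at 18/12 or 20/14, and about 5 at 20/10.
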